16.1 Appendix 1: Clinically notable laboratory values and vital signs

Table 16-1 Criteria For Notable Laboratory Abnormalities

Notable Values		
Laboratory Variable	Standard Units	SI Units
Serum glutamic oxaloacetic transaminase (SGOT) (AST)	>82 U/L	>82 U/L
Serum glutamic pyruvic transaminase (SGPT) (ALT)	>90 U/L	>90 U/L
Total bilirubin	≥ 2.0 mg/dL	≥ 34.2 µmol/L
RENAL FUNCTION / METABOLIC VARIABLES		
Creatinine	≥2.0 mg/dL	≥176umol/L
Cholesterol	≥ 240 mg/dL	≥ 6.21 mmol/L
Triglycerides	≥ 300 mg/dL	≥ 3.39 mmol/L
HEMATOLOGY VARIABLES		
Hemoglobin	≤ 10.0 g/dL	≤ 100g/L
Platelets (Thrombocytes)	≤ 100 k/mm ³	≤ 100 x 10 ⁹ /L
	≥ 600 k/mm ³	≥ 600 x 10 ⁹ /L
Leukocytes (WBCs)	≤ 2.0 k/mm ³	≤ 2.0 x 10 ⁹ /L
	≥ 15 k/mm ³	≥ 15x 10 ⁹ /L
HEMATOLOGY VARIABLES: DIFFERENTIAL		
Granulocytes (Poly, Neutrophils)	≤ 1,000/mm ³	≤ 1 x 10 ⁹ /L
	≥12000/mm ³	≥ 12 x 10 ⁹ /L
Lymphocytes	<200/mm ³	<0.2 x 10 ⁹ /L
	≥8000/mm ³	≥8 x 10 ⁹ /L
Red blood cells (RBCs)	<3,300,000/mm ³	<3.3 x 10 ¹² /L
	>6,800,000/mm ³	>6.8 x 10 ¹² /L

NOTABLE VITAL SIGNS AND BODY WEIGHT	
Vital Sign Variable	Notable Criteria
Pulse (beats/min)	>120bpm or Increase of ≥ 15bpm from baseline Or < 50bpm or Decrease of ≥ 15bpm from baseline
Systolic BP (mmHg)	≥ 160 mmHg or Increase of ≥ 20mmHg from baseline Or ≤ 90 mmHg or Decrease of ≥ 20mmHg from baseline
Diastolic BP (mmHg)	≥ 100 mmHg or Increase of ≥ 15mmHg from baseline Or ≤ 50 mmHg or Decrease of ≥ 15mmHg from baseline
Temperature (°C)	>38.3 °C/ 101°F

Body weight (kg)	$\pm 7\%$ from baseline weight
------------------	--------------------------------

16.2 Appendix 2 New York Heart Association Functional Classification

Class I	Patients have cardiac disease but without the resulting limitations of physical activity. Ordinary physical activity does not cause undue fatigue, palpitation, dyspnea, or anginal pain.
Class II	Patients have cardiac disease resulting in slight limitation of physical activity. They are comfortable at rest. Ordinary physical activity results in fatigue, palpitation, dyspnea, or anginal pain.
Class III	Patients have cardiac disease resulting in marked limitation of physical activity. They are comfortable at rest. Less than ordinary physical activity causes fatigue, palpitation, dyspnea, or anginal pain.
Class IV	Patients have cardiac disease resulting in inability to carry on any physical activity without discomfort. Symptoms of cardiac insufficiency or of the anginal syndrome may be present even at rest. If any physical activity is undertaken, discomfort is increased.

16.3 Appendix 3 McDonald criteria

Clinical Presentation	Additional Data Needed for MS Diagnosis
no less than 2 attack ^a ; objective clinical evidence of ≥ 2 lesions or objective clinical evidence of 1 lesion with reasonable historical evidence of a prior attack ^b	None ^c
no less than 2 attack ^a ; objective clinical evidence of 1 lesion	Dissemination in space, demonstrated by: ≥ 1 T2 lesion in at least 2 of 4 MS-typical regions of the CNS (periventricular, juxtacortical, infratentorial, or spinal cord) ^d ; or Await a further clinical attack ^a implicating a different CNS site
1 attack ^a ; objective clinical evidence of ≥ 2 lesions	Dissemination in space, demonstrated by: Simultaneous presence of asymptomatic gadolinium-enhancing and nonenhancing lesions at any time; or A new T2 and/or gadolinium-enhancing lesion(s) on follow-up MRI, irrespective of its timing with reference to a baseline scan; or Await a second clinical attack ^a
1 attack ^a ; objective clinical evidence of 1 lesion (clinically isolated syndrome)	Dissemination in space, demonstrated by: For DIS: ≥ 1 T2 lesion in at least 2 of 4 MS-typical regions of the CNS (periventricular, juxtacortical, infratentorial, or spinal cord) ^d ; or Await a second clinical attack ^a implicating a different CNS site; and Dissemination in time, demonstrated by: For DIT: Simultaneous presence of asymptomatic gadolinium-enhancing and nonenhancing lesions at any time; or A new T2 and/or gadolinium-enhancing lesion(s) on follow-up MRI, irrespective of its timing with reference to a baseline scan; or Await a second clinical attack ^a
Insidious neurological progression suggestive of MS(PPMS)	1 year of disease progression (retrospectively or prospectively determined) plus 2 of 3 of the following criteria ^d : 1. Evidence for DIS in the brain based on ≥ 1 T2 lesions in the MS-characteristic (periventricular, juxtacortical, or infratentorial) regions 2. Evidence for DIS in the spinal cord based on ≥ 2 T2 lesions in the cord 3. Positive CSF (isoelectric focusing evidence of oligoclonal bands and/or elevated IgG index)
If the Criteria are fulfilled and there is no better explanation for the clinical presentation, the diagnosis is "MS"; if suspicious, but the Criteria are not completely met, the diagnosis is "possible"	

Clinical Presentation	Additional Data Needed for MS Diagnosis
MS"; if another diagnosis arises during the evaluation that better explains the clinical presentation, then the diagnosis is "not MS."	
^a An attack(relapse; exacerbation) is defined as patient-reported or objectively observed events typical of an acute inflammatory demyelinating event in the CNS, current or historical, with duration of at least 24 hours, in the absence of fever or infection. It should be documented by contemporaneous neurological examination, but some historical events with symptoms and evolution characteristic for MS, but for which no objective neurological findings are documented, can provide reasonable evidence of a prior demyelinating event. Reports of paroxysmal symptoms (historical or current) should, however, consist of multiple episodes occurring over not less than 24 hours. Before a definite diagnosis of MS can be made, at least 1 attack must be corroborated by findings on neurological examination, visual evoked potential response in patients reporting prior visual disturbance, or MRI consistent with demyelination in the area of the CNS implicated in the historical report of neurological symptoms.	
^b Clinical diagnosis based on objective clinical findings for 2 attacks is most secure. Reasonable historical evidence for 1 past attack, in the absence of documented objective neurological findings, can include historical events with symptoms and evolution characteristics for a prior inflammatory demyelinating event; at least 1 attack, however, must be supported by objective findings.	
^c No additional tests are required. However, it is desirable that any diagnosis of MS be made with access to imaging based on these Criteria. If imaging or other tests(for instance, CSF) are undertaken and are negative, extreme caution needs to be taken before making a diagnosis of MS, and alternative diagnoses must be considered. There must be no better explanation for the clinical presentation, and objective evidence must be present to support a diagnosis of MS.	
^d Gadolinium-enhancing lesions are not required; symptomatic lesions are excluded from consideration in participants with brainstem or spinal cord syndromes.	
MS=multiple sclerosis; CNS=central nervous system; MRI=magnetic resonance imaging; DIS=dissemination in space; DIT=dissemination in time; PPMS=primary progressive multiple sclerosis; CSF=cerebrospinal fluid; IgG=immunoglobulin G.	

16.4 Appendix 4 EDSS Assessment Criteria

EXPANDED DISABILITY STATUS SCALE

0 = normal neurological exam (all FS grade 0)

1.0 = no disability, minimal signs in one FS (one FS grade 1)

1.5 = no disability, minimal signs in more than one FS (more than one FS grade 1)

2.0 = minimal disability in one FS (one FS grade 2, others 0 or 1)

2.5 = minimal disability in two FS (two FS grade 2, others 0 or 1)

3.0 = moderate disability in one FS (one FS grade 3, others 0 or 1) though fully ambulatory; or mild disability in three or four FS (three/four FS grade 2, others 0 or 1) though fully ambulatory

3.5 = fully ambulatory but with moderate disability in one FS (one FS grade 3) and mild disability in one or two FS (one/two FS grade 2) and others 0 or 1;

or fully ambulatory with two FS grade 3 (others 0 or 1);

or fully ambulatory with five FS grade 2 (others 0 or 1)

4.0 = ambulatory without aid or rest for ≥ 500 meters; up and about some 12 hours a day despite relatively severe disability consisting of one FS grade 4 (others 0 or 1) or combinations of lesser grades exceeding limits of previous steps

4.5 = ambulatory without aid or rest for ≥ 300 meters; up and about much of the day, characterized by relatively severe disability usually consisting of one FS grade 4 and combination of lesser grades exceeding limits of previous steps

5.0 = ambulatory without aid or rest for ≥ 200 meters (usual FS equivalents include at least one FS grade 5, or combinations of lesser grades usually exceeding specifications for step 4.5)

5.5 = ambulatory without aid or rest for ≥ 100 meters

6.0 = unilateral assistance (cane or crutch) required to walk at least 100 meters with or without resting

6.5 = constant bilateral assistance (canes or crutches) required to walk at least 20 meters without resting

7.0 = unable to walk 5 meters even with aid, essentially restricted to wheelchair; wheels self and transfers alone; up and about in wheelchair some 12 hours a day

7.5 = unable to take more than a few steps; restricted to wheelchair; may need some help in transferring and in wheeling self

8.0 = essentially restricted to bed or chair or perambulated in wheelchair, but out of bed most of day; retains many self-care functions; generally has effective use of arms

8.5 = essentially restricted to bed much of the day; has some effective use of arm(s);

retains some self-care functions

9.0 = helpless bed patient; can communicate and eat

9.5 = totally helpless bed patient; unable to communicate effectively or eat/swallow

10.0 = death due to MS

16.5 Appendix 5 Guidance for Monitoring of patients taking their first dose of the study drug

At treatment initiation, fingolimod induces a dose dependent reduction in heart rate (by approximately 12-13 bpm at 0.5 mg) that is maximal within 6 hours after the first dose administration, and then attenuates over days to weeks with continued dosing. This effect is asymptomatic in the vast majority of patients. No medical intervention to treat that effect was needed in any of the patients in the Phase II and III MS trials. Concomitant changes on the ECG/Holter were restricted to transient second degree type I atrio-ventricular block (Wenckebach) of benign nature, on day 1 of treatment. One case of third degree atrio-ventricular block 3 hours after first dose administration of fingolimod 1.25 mg was reported. This incident was self-limiting without symptoms, no sequelae and lasted 30 seconds. Please see Investigator Brochure for more details. As such, the following guidelines have been put in place to support the safe initiation of therapy with fingolimod.

At the Day 1 visit, participant enroll into this study is naive participant who has never use fingolimod before recruitment, so first dose administration monitoring will be mandatory on-site monitoring as described below.

Pre-dose ECG should be provided by the site and be available for comparison to the post-dose ECG in order to determine if discharge criteria are met. Sitting heart rate and blood pressure should be measured prior to the 1st dose of the study drug then every hour for at least 6 hours thereafter (by the First Dose Administrator). When obtaining the pre-dose heart rate prior to the 1st dose intake, the participant should be allowed to rest sitting for 5 minutes. Then the sitting heart rate should be taken. The sitting heart rate and blood pressure measurements should be collect three times to produce three baseline readings for both heart rate and blood pressure (prior to the 1st dose of the study drug only). For comparison to the post-dose heart rate values, the lowest pre-dose value of heart rate should be used. Participants should receive the first dose of the study drug before 12:00 PM (noon) in the outpatient setting. Participants may be discharged after 6 hours ONLY if ALL of the following discharge criteria are met.

- Heart rate at discharge must be at least 51 bpm (in patient 18 years or older), 55 bpm (in patients 12 years or older) or 60 bpm (in children \geq 10 years and below 12)
- Heart rate at discharge must be greater than 80% of baseline value ([Table 16-2](#) below)
- Heart rate at discharge must not be the lowest hourly value measured during the observation period (which would be suggestive of a continuing progressive decline in heart rate)
- Participants must have no symptoms associated with decreased heart rate
- ECG at 6 hours should not show any new significant abnormalities other than sinus bradycardia not observed at the patient's pre-dose ECG

Participants should have written instruction on when to return to clinic and a 24 hour contact phone number to call in the event of any new or warranted symptoms (chest pain, dizziness, palpitations, syncope, nausea and vomiting, etc.). Participants should be instructed not to drive themselves after the first dose of study drug administration.

Participants whose heart rate drops by more than 30% (as a result of strong sensitivity to the study drug) from pre-dose at any time during the 6-hour monitoring period may be discharged,

provided they meet the discharge criteria, but must return on Study Day 2 to take the second dose of the study drug and must be monitored as on Study Day 1.

If the above discharge criteria are not met, participants should continue to be observed until they are met. Participants experiencing any symptomatic event associated with reduction of the heart rate in the first 24 hours must take the Day 2 dose of study drug at the study center and must be monitored hourly for 6 hours before discharge. After the 6 hour monitoring participants may be discharged only if they meet the discharge criteria described above.

Table 16-2 Heart rate table for cardiac release criteria

Baseline Heart Rate	Minimum HR at 6hr post 1 st dose of the study drug eligible for release	HR reduction within 6hr monitoring indicating need for monitoring after 2 nd dose
45	40	31
46	40	32
47	40	33
48	40	33
49	40	34
50	40	35
51	40	35
52	41	36
53	42	37
54	43	38
55	44	39
56	45	39
57	45	40
58	46	41
59	47	41
60	48	43
61	49	43
62	50	43
63	50	44
64	51	45
65	52	46
66	53	46
67	54	47
68	54	48
69	55	48
70	56	49
71	57	50
72	58	50
73	58	51
74	59	52
75	60	53

Baseline Heart Rate	Minimum HR at 6hr post 1 st dose of the study drug eligible for release	HR reduction within 6hr monitoring indicating need for monitoring after 2 nd dose
76	61	53
77	62	54
78	62	55
79	63	55
80	64	56
81	65	57
82	66	57
83	66	58
84	67	59
85	68	60
86	69	60
87	70	61
88	70	62
89	71	62
90	72	63
91	73	64
92	74	64
93	74	65
94	75	66
95	76	67
96	77	67
97	78	68
98	78	69
99	79	69
100	80	70
101	81	71
102	82	71
103	82	72
104	83	73
105	84	74
106	85	74
107	86	75
108	86	76
109	87	76
110	88	77
111	89	78
112	90	78
113	90	79
114	91	80

Baseline Heart Rate	Minimum HR at 6hr post 1 st dose of the study drug eligible for release	HR reduction within 6hr monitoring indicating need for monitoring after 2 nd dose
115	92	81
116	93	81
117	94	82
118	94	83
119	95	83
120	96	84
121	97	85
122	98	85
123	98	86
124	99	87
125	100	88
126	101	88
127	102	89
128	102	90
129	103	90
130	104	91

Recommendations for management of bradycardia

Clinicians should be particularly mindful of participants who have a low heart rate at pre-dose (spontaneously or through drug induced β -receptor blockade), prior to administration of the study drug.

Atropine (sc or iv) is recommended as the first line treatment of bradycardia, up to a maximum daily dose of 3 mg.

Furthermore, the common guidelines for treatment of bradycardia (e.g. ACLS guidelines) should be followed as appropriate:

- In case of clinical symptoms or hypotension, administration of atropine 1 mg, repeated administration in 3-5 minutes
- If heart rate and/or blood pressure remains unresponsive, consider administration of dopamine drip 5-20 ug/kg/min or epinephrine drip 2-10 ug/min
- Performance of transcutaneous pacing may also be considered

In the setting of decreased blood pressure, isoproterenol should be avoided/used with caution.

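### The release column of Protocol Table 16-2 prints first-dose discharge heart rates below the age minimum in the governing text, and often not above 80% of baseline (minor)

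*Protocol*

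**What the plan says.** Protocol 16.5 (Appendix 5, first-dose monitoring) joins its discharge criteria strictly: "Participants may be discharged after 6 hours ONLY if ALL of the following discharge criteria are met". Two of them set heart-rate limits:

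- An absolute minimum by age: "Heart rate at discharge must be at least 51 bpm (in patient 18 years or older), 55 bpm (in patients 12 years or older"), and 60 bpm for children from 10 to below 12 years.
- A relative minimum: "Heart rate at discharge must be greater than 80% of baseline value". Table 16-2 is cited here and at no other criterion.

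The remaining criteria are that the discharge rate is not the lowest hourly value, that there are no symptoms of a reduced heart rate, and that the 6-hour ECG shows no new significant abnormality other than sinus bradycardia.

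For a participant who fails, the text is explicit: "If the above discharge criteria are not met, participants should continue to be observed until they are met". The sentence just before the table, on monitoring of the Day 2 dose, repeats the rule: "After the 6 hour monitoring participants may be discharged only if they meet the discharge criteria described above".

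Table 16-2 is titled "Heart rate table for cardiac release criteria". Its middle column gives, for each baseline from 45 to 130 bpm, the minimum 6-hour rate after the first dose "of the study drug eligible for release". It has no age column and no note that the age minimum also applies.

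**The concern.** The title and column heading present the table as the release threshold, not as a lookup for one criterion among several. Yet at low baselines the printed values lie under the absolute minimum that the text requires.

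The table is not a pure 80% lookup either. At baselines 45-49 it prints 40 bpm, where 80% would be 36.0 to 39.2. That is an absolute floor which appears in no criterion and differs from 51, 55 and 60. A reader who sees a floor built in may assume that the absolute minimum has been dealt with.

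At stake is a first-dose safety instruction. The protocol names bradyarrhythmia after the first dose as a known risk, and Section 16.5 asks clinicians to take particular care with a low pre-dose rate. The low-baseline rows are where table and text differ most. The same monitoring is repeated after qualifying interruptions, so the table can be used more than once per participant.

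**Working it through.** **Inputs.** All 86 rows of Table 16-2 (baseline 45 to 130); age minimums of 51, 55 and 60 bpm; the rule of greater than 80% of baseline; the expected first-dose effect, a "reduction in heart rate (by approximately 12-13 bpm at 0.5 mg"). All are from Protocol 16.5.

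**Step 1: reproduce the column.** The larger of 40 and 0.80 × baseline, rounded to the nearest bpm, gives 83 of the 86 printed entries. The other three are 1 bpm lower: baseline 51 (40.8, printed 40), 52 (41.6, printed 41) and 57 (45.6, printed 45). So the column is an 80% rule with a floor of 40, and age does not enter it.

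**Step 2: compare with the age minimum.**

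| Age group | Minimum (bpm) | Baselines with a lower entry | Rows of 86 | Last such row |
|---|---|---|---|---|
| 18 or older | 51 | 45-63 | 19 | 63, printed 50 |
| 12-17 | 55 | 45-68 | 24 | 68, printed 54 |
| 10-11 | 60 | 45-74 | 30 | 74, printed 59 |

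**Step 3: compare with greater than 80%.** 17 entries equal 0.80 × baseline (for example 100, printed 80). 35 are below it; the largest shortfall is at baseline 51, 40.8 − 40 = 0.8 bpm. Together 17 + 35 = 52 entries are not strictly above 80%, and 86 − 52 = 34 are.

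**Step 4: combine the two limits.** The smallest whole bpm that satisfies both is max(age minimum, floor(0.80 × baseline) + 1). The printed entry is too low in 60 rows for adults, 62 for ages 12-17 and 64 for ages 10-11, and is never too high. These counts split as follows:

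- Adults: 19 below the age minimum + 41 that meet it but are 1 bpm short of exceeding 80% = 60.
- Ages 12-17: 24 + 38 = 62.
- Ages 10-11: 30 + 34 = 64.

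**Step 5: a reader who uses only the table.** Such a reader releases when baseline − fall ≥ table entry. The age minimum fails when baseline − fall < 51, 55 or 60. Baselines where both hold:

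| 6-hour fall | Adults | Ages 12-17 | Ages 10-11 |
|---|---|---|---|
| 11 bpm | 51-61 (11) | 51-65 (15) | 51-70 (20) |
| 12 bpm | 57-62 (6) | 57-66 (10) | 57-71 (15) |
| 13 bpm | 63 (1) | 63-67 (5) | 63-72 (10) |

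These are table rows, not patient frequencies, and the lowest-hourly-value, symptom and ECG criteria have not been applied.

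**Step 6: a case where only the age minimum fails.** Take an adult with baseline 62, a lowest hourly value of 49, and 50 at 6 hours, with no symptoms and no new ECG finding. The ratio is 50/62 = 0.806, above 80%. The table entry is 50, so the table says release. The text says keep observing, because 50 < 51.

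**Step 7: the second-dose column.** The text asks for second-dose monitoring after a fall of more than 30%, that is, below 70% of baseline. At baseline 60, 0.70 × 60 = 42, but 43 is printed. The error is in the cautious direction. Every other row is within 0.7 bpm of 70%.

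**The case against.** The strongest reply is that the documents contain no competing rule. All criteria must hold together, the age minimum is the first of them, the table is cited only at the 80% criterion, and the sentence just before the table repeats the requirement. Protocol 6.7.2 and 8.4.4.1 also send the reader to the discharge criteria in Section 16.5, not to the table. A lookup for one joint criterion need not restate the others. This stands, and it fixes the grade.

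A reader might infer that the protocol authorises release at 40 to 50 bpm, or that participants were released too early. The documents support neither. The text forbids such a release, and nothing shows that any site worked from the table alone or that a dose-monitoring form reproduces it.

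The criterion on the lowest hourly value narrows the exposure further. Protocol 1.1 places the mean maximal fall at about 6 hours, and a participant whose 6-hour rate is the lowest so far stays under observation anyway.

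The reply does not reduce the point to a missing footnote. Even as a lookup for the 80% criterion, the column is not strictly above 80% in 52 rows, so a site that applies every criterion but reads the 80% limit from the table can also be slightly low. That shortfall is at most 0.8 bpm, which is trivial clinically, but the printed threshold is still wrong.

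**Conclusion.** The point holds as a minor error in a printed safety threshold. The release column lies below the age minimum in 19, 24 and 30 of 86 rows (adults, ages 12-17, ages 10-11) and is not strictly above 80% of baseline in 52.

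The consequence depends on how a site uses the table. With every criterion applied, the age minimum is respected and only the sub-1-bpm shortfall on the 80% rule remains. With the table alone, release below the age minimum is possible. At a 6-hour fall of 12 to 13 bpm, the size the protocol expects, this concerns 6 and 1 adult baselines, 10 and 5 for ages 12-17, and 15 and 10 for ages 10-11. Those counts assume whole-bpm readings. They say nothing about how many participants have such baselines, which the documents do not report.

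The 40 bpm floor at baselines 45-49 matches no criterion but is stricter than 80%, and it has no effect where the age minimum is applied. The ARR analysis and the sample size are unaffected.

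**What to change.** Replace the release column, by age group, with max(age minimum, smallest whole bpm above 80% of baseline):

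- Adults: 51 for baselines 45-63, then 52 at 64 and rising.
- Ages 12-17: 55 for baselines 45-68, then 56 at 69 and rising.
- Ages 10-11: 60 for baselines 45-74, then 61 at 75 and rising.

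Correct the second-dose entry at baseline 60 from 43 to 42. Notify sites, and check whether any dose-monitoring form reproduces the table.

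The notice should settle one consequence. Where the baseline is itself below the age minimum (adults 45-50, ages 12-17 45-54, ages 10-11 45-59), the new column asks for a rate above the participant's own baseline. The text already requires this; the sponsor should confirm that it is intended.

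A cheaper alternative is a footnote saying that all discharge criteria apply, including the age minimum and a rate strictly above 80% of baseline. That leaves the wrong entries in print.

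The cost is one appendix table and a site notice, plus slightly longer observation for some low-baseline participants at sites that had used the table alone. There is no statistical cost.
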